#### 6.2.3 Follow-up Visits

N/A-there are no follow-up visits since we are using secondary Medicare claims data to measure our primary outcome.

#### 6.2.4 Completion/Final Evaluation

##### Patient Subjects:

We will not assess Medicare beneficiaries at a clinic visit. Rather, the primary outcome (Specific Aim #1) and one of the secondary outcomes (Specific Aim #2) will be evaluated using secondary Medicare claims data 12 months after completion of the clinician value champion training program.

**Clinician Subjects:**

A clinician value champion will have completed the study once the training and shared learning sessions are over. If they have chosen to participate in the interviews, they will have completed the study once the second interview is complete.

## **7 SAFETY ASSESSMENTS**

### **7.1 Specification of Safety Parameters**

There are no known risks to discontinuing these potentially inappropriate medications. Instead, the purpose of discontinuing these medications is to lower the risk of an adverse event due to the medication such as a fall, changes in cognitive status, or acceleration of the course of dementia. In addition, the data used to measure the primary outcome, pharmacy claims data, is de-identified and contains no PHI, lowering the risk due to loss of confidentiality.

These three classes of medication pose significant risks to older patients with dementia including falls, changes in cognitive status, and potentially accelerating the course of their dementia. The risk of these adverse events is significantly lowered by discontinuing these medications. Each of the risks described above also has the potential to create a cascade of adverse experiences such as fractures or head trauma from falls, resulting in hospitalization and the need for skilled nursing care instead of returning home.

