## **2 ADDITIONALLY, DATA COLLECTED THROUGH TWO INTERVIEWS WITH APPROXIMATELY 8 CLINICIAN VALUE CHAMPIONS WILL PROVIDE US WITH THE MEASURES WE NEED TO ASSESS FIVE IMPLEMENTATION OUTCOMES: APPROPRIATENESS, FIDELITY, FEASIBILITY, PENETRATION AND EQUITY.**

### **BACKGROUND AND RATIONALE**

#### **2.1 Background on Condition, Disease, or Other Primary Study Focus**

For people living with dementia (PLWD) the overuse of Potentially Inappropriate Medications (PIMs), those for which the potential for harm outweighs benefit, remains a persistent problem despite evidence-based guidelines supporting their de-adoption. A group of geriatric experts convened by the Choosing Wisely initiative identified three classes of PIMs for PLWD: antipsychotics, benzodiazepines, and hypoglycemics (sulfonylureas and insulin) with adequate glycemic control. In a systematic review the prevalence of PIMs when cognitive impairment was reported ranged from 20.6% to 80.5%. Approximately 14.3% of Medicare Part D enrollees with dementia residing in the general community are prescribed an antipsychotic. The prevalence of potentially inappropriate benzodiazepine prescriptions has been reported to be as high as 20% among elderly persons with dementia living in the community. The proportion of elderly patients with an A1c < 7% who received a prescription for sulfonylurea, insulin or combined insulin and sulfonylurea therapies was 35.2%, 24.2% and 16.3% respectively and was as prevalent in those with dementia as in those without. Park and colleagues compared rates of prescribing low-value medications in the elderly from 2006-2015 in both traditional Medicare and Medicare Advantage. Not only was there no difference in rates between the two groups, there was also no evidence of any decline in rates of prescribing over time, including use of benzodiazepines in PLWD.

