Training and supporting a clinician value champion is a simple and pragmatic approach that any health system can deploy to address overuse of PIMs in their PWLD population. They are front-line clinicians who can advocate for and influence practice-driven change and may be particularly effective in de-implementing PIMs because they can: 1) be a trusted source of information about the potential harms of PIMs, 2) provide feedback and discuss prescribing behaviors with their colleagues, 3) serve as a role model for how to

provide guideline-concordant care for PLWD, and 4) identify contextual barriers and facilitators and leverage them to reduce PIMs use in their local setting. The clinician champion model is widely recognized as effective in implementing evidence-based practices in health care settings.

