##### Clinician Subjects:

Clinical leaders at the two ACOs with an understanding of the scope of the project will identify and approach clinicians at each intervention clinic to take part in the Value Champions training sessions. Clinical leadership will support VCs participation in the project in re: time needed for training and de-implementation efforts.

The clinician VCs are the de-implementation intervention. The control group (clinics) have no clinician VC embedded at the clinic. We will conduct 2 interviews with approximately 8 VCs that have completed the webinar training to measure implementation outcomes. Each VC who agrees to be interviewed will be interviewed approximately 5-7 months after webinar training is complete, and a second time approximately 10-12 months after training is complete. The implementation measures are not used to assess the VCs themselves (no personal information, or health information about the VCs will be collected). These interviews will be analyzed to provide insight into the de-implementation process at each ACO; how the de-implementation intervention was tailored and taken up in the clinical setting, for example. We will report each implementation outcome, both within each ACO and across the two ACO.

An email with an information sheet attached will be sent to the Value Champions after they are identified by clinical leaders, and before the first Webinar training. Included in this email is contact information to ask questions. At the first Webinar training session, we will start

the meeting by reminding Value Champions about the information sheet, ask if there are questions, and provide contact information to use in order to ask questions privately.

We are requesting a waiver of documentation of consent to enrolled clinician Value Champions in the study.

We will mention the interviews to the clinician champions during the monthly shared learning phone calls, and in emails reminding the group of the upcoming phone calls. We will then send an email inviting the clinician Value Champions to participate, with an information sheet explaining the interviews. The email and information sheet will note that they may opt out of the interviews. The email and information sheet will also give contact information if the clinicians have questions about the interviews.

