### **7.2 Methods and Timing for Assessing, Recording, and Analyzing Safety Parameters**

As data used to measure the primary outcome is de-identified, contains no PHI, and is collected after the intervention is completed. However, to ensure that we capture any unexpected AEs, we will ask each clinician champion to monitor for any unexpected adverse events and complete an adverse event form if they see one. Once each month, clinician value champions will be asked to send all adverse event forms to the study coordinator. No SAEs are expected as described above. All deaths within the study cohort will also be reported along with a cause of death

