### **7.3 Adverse Events and Serious Adverse Events**

**AE Definition:** AE is any untoward or unfavorable medical occurrence in a human study participant, including any abnormal sign (e.g. abnormal physical exam or laboratory finding), symptom, or disease, temporally associated with the participants' involvement in the research, whether or not considered related to participation in the research.

**AEs for this study include:** There are no known expected or unexpected adverse events. Rather, discontinuing these medications lowers the risk of an adverse event from these medications.

**SAE Definition:** SAEs consist of any adverse event that results in death; is life threatening or places the participant at immediate risk of death from the event as it occurred; requires or prolongs hospitalization; causes persistent or significant disability or incapacity; results in congenital anomalies or birth defects; is another condition which investigators judge to represent significant hazards

**SAEs for this study include:** None

As there are no expected AEs or SAEs, we will not capture solicited AEs or SAEs. Unsolicited AEs and SAEs will be noted during clinical care. Once each month, clinician value champions will be asked to send all adverse event forms to the study coordinator. No SAEs are expected as described above. All deaths within the study cohort will also be reported along with a cause of death

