### 7.4 Safety Monitoring

The Principal Investigator (PI) will be responsible for ensuring participants' safety on a daily basis. In addition, the NIA IMPACT Collaboratory DSMB will oversee all data and safety monitoring activities for this study. The number of DSMB members will be determined by NIA, and one will be designated the Chairperson. DSMB members will be appointed by the NIA Director. This DSMB will act in an advisory capacity to the NIA Director to monitor participant safety, to evaluate the progress of the study, and to review procedures for maintaining the confidentiality of data, the quality of data collection, management, and analyses. Advarra IRB will conduct the ethical review required for the protection of human subjects. NIA PO, in consultation with DSMB chair, will make a determination regarding the level and format of data and safety monitoring this study requires.

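### The safety section declares stopping all three drug classes free of known risk, although the background qualifies the hypoglycemic class by glycemic control, and no two-arm count of non-fatal glycemic emergencies is planned

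*Combined protocol and SAP*

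**What the plan says.** Section 7.1 opens with "There are no known risks to discontinuing these potentially inappropriate medications". It does not separate the classes, and its next paragraph speaks of all three together. Section 7.3 draws the consequence: "As there are no expected AEs or SAEs, we will not capture solicited AEs or SAEs".

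Section 2.1 describes the third class as "hypoglycemics (sulfonylureas and insulin) with adequate glycemic control". The overtreatment prevalence it cites is for patients with A1c below 7%.

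The plan does provide some safety capture:

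- Section 7.2: "we will ask each clinician champion to monitor for any unexpected adverse events and complete an adverse event form if they see one". The forms go to the study coordinator monthly.
- Section 7.2 also says: "All deaths within the study cohort will also be reported along with a cause of death".
- Section 7.3.2 sends serious, unexpected events to the IRB, the NIA program officer and the DSMB chair within 48 hours of the study's knowledge. Other SAEs are summarized quarterly.
- Section 7.4 says that the NIA program officer, in consultation with the DSMB chair, "will make a determination regarding the level and format of data and safety monitoring this study requires".

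Section 4.3 states: "The control group (clinics) have no clinician VC embedded at the clinic".

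**The concern.** For one of the three primary classes, the safety premise is broader than the background's own description of when the drugs are inappropriate. The MPR counts any fall in sulfonylurea or insulin supply as movement in the intended direction, whether or not the patient met the glycemic-control condition. If the intervention lowers this MPR, a reader will want to know whether glycemic emergencies went up or down in the intervention arm relative to control. The plan offers no figure for that. Passive reports from one arm cannot show an excess over the other.

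The stake is limited. Section 9.1 describes a demonstration project on feasibility and acceptability. The point concerns the safety wording and one descriptive safety estimate.

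**Working it through.** **Step 1. Where the glycemic-control condition appears.**

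- Background (2.1): stated, with prevalence tied to A1c below 7%.
- Patient eligibility (sections 3, 4.1, 4.2): visit claim, Parts A, B and D coverage, dementia codes, metastatic cancer, hospice. No glycemic criterion.
- Primary outcome (3, 9.4.1): days supply filled in the class over the length of the quarter. No glycemic criterion.
- Analysis (9.1, 9.4.2, 9.5): all dementia-eligible beneficiaries, with age and sex as the named key covariates. No glycemic variable or subset.
- Data sources (10.1): Medicare claims and clinician interviews. No A1c data are mentioned.

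So the condition is stated once and not used again.

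**Step 2. Which safety data exist in both arms.**

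- Champion forms: intervention clinics only, because control clinics have no champion.
- Unsolicited events noted in care (7.3): the only collection route described is the champions' monthly forms.
- Deaths with cause: the whole cohort, read here as both arms. A fatal glycemic event could appear.
- Falls (6.1, 9.4.2): both arms, from claims. A glycemic event that led to a coded fall would appear as a fall.

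Non-fatal glycemic emergencies therefore have no planned two-arm count.

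**Step 3. How precise an added count would be.** The plan states no figure for this outcome. Its MPR power does reproduce (1,600 per group, 0.10 SD, two-sided 5%: 80.7% against the stated 80%), but that does not bear on this point.

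Inputs from the documents: 2,000 + 500 = 2,500 patients per arm (9.2); 32 USMM and 26 Ochsner practices, 58 in all (9.2.1).

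Assumptions, since the documents give none of these: 10% to 30% of patients use a sulfonylurea or insulin; 2% to 5% of users have a glycemic emergency in a year; ICC 0 to 0.02. As a share of all patients this is 10% × 2% = 0.2% up to 30% × 5% = 1.5%, or 5 to 37.5 events per arm.

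Design effect = 1 + (m − 1) × ICC.

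- Equal clinic sizes: m = 5,000/58 = 86.2. At ICC 0.02, 1 + 85.2 × 0.02 = 2.70.
- Unequal sizes: 4,000/32 = 125 per USMM practice and 1,000/26 = 38.46 per Ochsner practice. Size-weighted m = (32 × 125² + 26 × 38.46²)/5,000 = 107.7. At ICC 0.02, 1 + 106.7 × 0.02 = 3.13.

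95% half-width = 1.96 × √(2p(1 − p) × design effect / 2,500), in percentage points (share of base rate):

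- p = 0.2%: ICC 0, 0.25 (124%); ICC 0.02 equal, 0.41 (204%); ICC 0.02 unequal, 0.44 (219%).
- p = 0.5%: 0.39 (78%); 0.64 (129%); 0.69 (138%).
- p = 1.0%: 0.55 (55%); 0.91 (91%); 0.98 (98%).
- p = 1.5%: 0.67 (45%); 1.11 (74%); 1.19 (80%).

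The range is thus about 45% to 219% of the base rate. Section 9.2 gives at least 30 USMM practices where 9.2.1 gives 32. With 30, size-weighted m is 114.4, the design effect 3.27 and the upper end 224%, so the picture is unchanged. At 5 events per arm the normal interval is rough, and raw counts must sit beside it.

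**The case against.** **The conflict is softer than it looks.** Section 2.1 does not say that hypoglycemics are inappropriate only under good control. Section 7.1 speaks of potentially inappropriate medications, which section 2.1 defines as drugs whose potential for harm outweighs benefit, so it could be read as carrying the condition with it. This stands in part: a reader might infer a flat contradiction, and the text does not force one. But 7.1 goes on to speak of the three classes as such, and the outcome counts all supply in the class, so the wording needs its qualifier.

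**Serious events already have a route.** A glycemic admission meets the SAE definition in 7.3, and the NIA program officer and DSMB chair can set more monitoring. This stands. A reader might infer that the plan collects no safety data, and that is wrong. The gap is only the two-arm comparison of non-fatal events, which section 7.4 does not promise.

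**Practice may respect the condition.** Champions are to model how to "provide guideline-concordant care for PLWD", and section 8 calls the deprescribing goal standard care. This also stands. The documents do not support an inference that champions will withdraw needed insulin, or that the intervention is unsafe. Equally, neither section says that the condition is checked.

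**The count does not cure the mismatch.** It cannot separate patients by glycemic control, is imprecise, and arrives after the intervention. A null table could be misread as reassurance. All true. Only the wording change addresses the mismatch directly; the count helps a reader interpret the MPR result.

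**Conclusion.** The point holds as a cheap improvement of low to moderate severity. The unqualified statement in 7.1, and the reliance on it in 7.3, do not match the qualifier in 2.1. The plan has no two-arm count of non-fatal glycemic emergencies for one of its three primary classes.

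The clinical link is an inference from the background's qualifier, since no section names glycemic events. The precision range rests on assumed user shares, event rates and ICC. Across those ranges only large excesses could be excluded, so the added figures are descriptive. A reader might infer that the primary MPR analysis is invalid; nothing here supports that, and the analysis does not change.

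**What to change.** 1. In 7.1, qualify the no-known-risk statement for sulfonylureas and insulin by the glycemic-control condition of 2.1. In 9.4.1, state that the MPR does not apply that condition. In 7.3.2, state that glycemic SAEs keep the 48-hour route, so that acknowledging a risk does not move them to the quarterly summary as expected events.
2. Add to the Aim 2 claims extraction (6.1, 9.4.2) ED visits or hospital stays for hyperglycemia and, separately, for hypoglycemia, by randomized arm over the same window as falls. Report raw counts and a pooled risk difference for each, with 95% intervals clustered on practice. Label them descriptive, with no tests and a note that a null result is not evidence of safety.
3. Do not add a subset of baseline users by default. Sections 3 and 4.1 apply the coverage criterion during the intervention year, while the précis applies it before the intervention starts, so Part D look-back data are not secured. If a subset is wanted, limit it to patients with confirmed Part D coverage in the look-back and give raw counts only.

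The cost is a few sentences, two ICD-10 code lists and one table from claims already being extracted for falls. The claims are analyzed after the intervention, so the counts do not protect patients in real time.

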### **7.2 Methods and Timing for Assessing, Recording, and Analyzing Safety Parameters**

As data used to measure the primary outcome is de-identified, contains no PHI, and is collected after the intervention is completed. However, to ensure that we capture any unexpected AEs, we will ask each clinician champion to monitor for any unexpected adverse events and complete an adverse event form if they see one. Once each month, clinician value champions will be asked to send all adverse event forms to the study coordinator. No SAEs are expected as described above. All deaths within the study cohort will also be reported along with a cause of death

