#### **4.3 Study Enrollment Procedures**

##### Patient Subjects

We will partner with two ACOs with primary care clinic locations. Prior to random assignment, we will stratify all clinics/practices based on high versus low historic prescribing rates, with the cut-point for inclusion in the study based on the distribution of overall rates for all 3 therapeutic classes using data for 2019-2020. These clinics will be randomized 1:1 to either the intervention or control arms of the study. We will work closely with leadership in each ACO over months 1-3 of the study to recruit an appropriate clinician from each clinic in the intervention arm of the study to participate in the study. A total of 30 clinicians across the two ACOs will participate in the intervention, with 30 clinics in the control group without a clinician value champion.

We will request a waiver of informed consent and waiver of HIPAA authorization for including patient data in this study. The intervention will be embedded within the health care system at the clinic level as a training program for clinicians. No patients will be recruited into this study. Although data from human subjects are involved, no contact will ever be made with patients as this project involves the use of secondary data only. Attempting to obtain authorization or consent would not be feasible as this study will involve a study population of an estimated 5,000 patients. Consent and authorization of patients for enrollment in this study would create bias, generate prohibitive study costs rendering the study unfeasible, and produce results that would not be generalizable to other health care organizations. Furthermore, contacting 5,000 subjects for written consent would increase the only risk for patients - breach of confidentiality. We will ensure subjects' protection against risk by following the measures outlined in the section below.

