### **9.2 Sample Size and Randomization**

Our sampling plan anticipates enrolling at least 30 of the 39 practices in USMM and 26 of the 28 practices in Ochsner. Based on Medicare enrollments of 39,000 members in USMM with a 20 percent dementia rate in 2019, and 10,000 members in Ochsner with approximately 10 percent of members diagnosed with dementia in 2019, we should have

at least 2,000 patients per treatment group for USMM and 500 patients per treatment group for Ochsner. For our primary outcome, with a follow-up period of one year and with mediation possession rates calculated per patient each quarter, we will have approximately 4 MPR observations per patient or 8,000 observations per group for USMM analyses and 2,000 per group for Ochsner. Even after assuming significant correlation across time within patient and modest correlation between patients within a practice, which will reduce effective sample sizes by 20%, we should have the equivalent of 6,400 observations per treatment group for our USMM analyses and 1,600 observations per treatment group for Ochsner.

The expectation of our intervention is that for each medication class, it will produce clinically relevant decreases in mean possession rates of 10% of a standard deviation. If the effect size is this large for a medication class and using a 5% level of significance, our Ochsner sample (with effective size of at least 1,600 per group) will have 80% power to discern a significant difference, while our larger USMM sample (with effective size of at least 6,400 per group) will have almost 100% power. Indeed, our USMM sample will have 80% power to find a significant difference, even if the effect size is only 5% of a standard deviation

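### Adverse event forms come only from intervention clinics, so they cannot support a between-arm comparison, and apart from falls no harm has a specified two-arm source

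*Combined protocol and SAP*

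**What the plan says.** Section 7.2 gives the collection method: "we will ask each clinician champion to monitor for any unexpected adverse events and complete an adverse event form if they see one". Section 7.3 gives the route, "Once each month, clinician value champions will be asked to send all adverse event forms to the study coordinator", and section 7.3.2 repeats it. Section 7.3 also limits what is collected: "As there are no expected AEs or SAEs, we will not capture solicited AEs or SAEs". Unsolicited events are to be noted in routine care, but the champion's form is the only described way for them to reach the study.

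On where champions work, section 4.3 (Clinician Subjects) states "The control group (clinics) have no clinician VC embedded at the clinic". Section 4.3 (Patient Subjects) describes 30 intervention clinics, "with 30 clinics in the control group without a clinician value champion".

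On deaths, sections 7.2, 7.3 and 7.3.2 share one commitment: "All deaths within the study cohort will also be reported along with a cause of death". Section 7.3.2 adds a 24-hour reporting clock that starts when the study learns of the death. None of these sections says how the study learns of a death in a control clinic, where cause of death comes from, or whether deaths are tabulated by arm.

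On falls, sections 1.2, 6.2.4 and 9.4.2 make them a secondary outcome taken from Medicare claims, to be evaluated 12 months after champion training ends. Section 9.5 specifies no analysis of death, all-cause hospitalization or all-cause ED use.

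**The concern.** A reporting system that exists in one arm only cannot separate events caused by the intervention from events that would have happened anyway. In an older population with dementia the background of deaths and admissions matters. Section 7.3.1 asks for each event to be graded for relatedness, yet the forms supply no concurrent control rate to judge against.

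Capture within the intervention arm is fragile too. It rests on one clinician per clinic, who knows the allocation and is leading the effort to reduce prescribing. Section 8 allows a champion to withdraw and be replaced only where feasible, so an intervention clinic may also lose its reporter.

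At stake is what the DSMB and the final report can say about harm other than falls. Section 7.1 asserts that stopping these medicines carries no known risk. As written, the plan tests that assertion against a control group for falls alone, and section 1 of the protocol treats falls as an outcome expected to improve.

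**Working it through.** The plan states no figure on this point, so the main check sets the sources of harm data side by side.

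| Harm | Source | Intervention arm | Control arm | Comparison by arm |
|---|---|---|---|---|
| AEs and SAEs on forms | Champion (7.2, 7.3, 7.3.2) | One reporter per clinic | No reporter (4.3) | Not possible |
| Fall-related ED visit or hospitalization | Medicare claims (1.2, 9.4.2) | Yes | Yes | Yes, after the project phase |
| Death | Not stated (7.2, 7.3, 7.3.2) | Promised | Promised | Not stated |
| All-cause hospitalization or ED visit | Not planned | No | No | None |

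**Share of patients without a reporter.** Section 9.2 expects "at least 2,000 patients per treatment group for USMM and 500 patients per treatment group for Ochsner". That gives 2,000 + 500 = 2,500 per arm and 2 × 2,500 = 5,000 in total. The control arm is 2,500 / 5,000 = 50% of patients. By clinics it is 30 of 60 under section 4.3; section 9.2.1 implies 32 + 26 = 58 eligible clinics, split in half. The control-arm count of champion forms is 0 whatever the true event rate, so the forms cannot yield a risk difference or ratio.

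**What a claims-based table could detect.** The documents give no safety event rate and no ICC. The following rests on assumed control rates of 2–20% and ICCs of 0–0.05, and is an illustration only.

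- Mean cluster size: m = 5,000 / 58 = 86.2.
- Design effect: DE = 1 + (m − 1) × ICC.
- Effective size per arm: n = 2,500 / DE.
- Power for two proportions, two-sided 5%: Φ[(|p₂ − p₁| − 1.96 × SE₀) / SE₁], where SE₀ uses the pooled proportion and SE₁ the separate ones. Solve for p₂ at 80% power.

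Example with p₁ = 5% and ICC = 0.01: DE = 1 + 85.2 × 0.01 = 1.85 and n = 2,500 / 1.85 ≈ 1,350. Solving gives p₂ = 7.6%, an excess of 2.6 percentage points.

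Smallest detectable excess, in percentage points:

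| Assumed control rate | ICC 0 (n = 2,500) | ICC 0.01 (n = 1,350) | ICC 0.02 (n = 925) | ICC 0.05 (n = 475) |
|---|---|---|---|---|
| 2% | 1.3 | 1.8 | 2.3 | 3.4 |
| 5% | 1.9 | 2.6 | 3.2 | 4.7 |
| 10% | 2.5 | 3.5 | 4.3 | 6.1 |
| 20% | 3.3 | 4.5 | 5.5 | 7.7 |

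**Which cohort the table needs.** The Précis (Sample Size and Population) and section 9.1 fix eligibility before the intervention. Sections 3 and 4.1 apply the clinic-visit, coverage and diagnosis criteria during the intervention year. If continuous coverage through that year is required, a patient who dies partway may fail the criterion and leave the analysis. A death table built on that cohort could miss the events it is meant to count.

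**The case against.** The strongest reply is that the plan does have two-arm safety information. Section 7.1 lists falls first among the adverse events of concern and describes how they lead on to fracture, head injury and admission. Fall-related ED visits and hospitalizations are compared between randomised arms from claims. This stands. A reader might infer from the form system that the trial's safety data have no control arm at all, or that the trial cannot show any harm; the falls outcome contradicts both.

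A reader might also infer that control-arm deaths will be zero by design. The documents do not support this. The commitment on deaths is separate from the forms and covers the whole cohort, which includes control patients. What is missing is the source and the comparison by arm.

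Third, no section proposes to compare form counts between arms. The forms are for unexpected events assessed case by case, and section 7.4 leaves the level and format of monitoring to the funder's program officer with the DSMB chair. This is fair: the forms can serve as case reports. But nothing else is specified for harms other than falls and deaths, and the protocol does not warn readers against comparing the counts.

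Finally, section 2.1 describes the target as "hypoglycemics (sulfonylureas and insulin) with adequate glycemic control", while the outcome definition carries no such limit. It is tempting to use that as support here. It is a separate question of outcome definition, and an all-cause safety table would not resolve it.

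**Conclusion.** The point holds in limited form. AE and SAE forms come from one arm only, reported by unblinded clinicians who deliver the intervention, and they leave about half of the expected 5,000 patients without a reporter. They cannot support a between-arm comparison. Apart from claims-based falls, and deaths whose source and comparison by arm are not stated, no harm is ascertained equally in both arms.

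This conclusion rests on reading the champion as the only reporter, because the protocol names no other. It would weaken if a control-clinic reporter or a two-arm source of death data existed in a document outside the protocol. The detectable-excess figures depend wholly on assumed rates and ICCs. They show that a claims table would be informative for moderate excesses and would not settle small ones.

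This does not threaten the primary analysis. It is a gap in safety reporting that can be largely closed at small cost.

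**What to change.** In sections 7.2 and 9.5:

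- Add a descriptive safety table by randomised arm over the 12-month project phase: all-cause death, all-cause hospitalization and all-cause ED visits from claims, with standard errors clustered by practice.
- Base it on the cohort fixed before the intervention (Précis and section 9.1), not on continuous coverage through the intervention year (sections 3 and 4.1), so that patients who die are kept. Reconcile those passages.
- Name the source of death data, and of cause of death, for both arms, and say when the study expects to learn of control-clinic deaths.
- Label champion reports as unsolicited, from the intervention arm only, and not for comparison.

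The cost is some wording and a few more tables. Section 10.1 shows that claims are already accessed for Aims 1 and 2; because it ties the data use agreements to those aims, the team should confirm that they also cover a safety table. There are two downsides. The table is available only after the intervention, so it cannot inform monitoring during the trial, and its precision is limited, so it should be presented as estimates with intervals and not as a test of safety.
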